## **G. TREATMENTS**

### **G.1 Standardization of Intervention**

#### **All Procedures:**

1. The participating study surgeons have been trained in and regularly perform esophagectomies with jejunostomy tube placement.
2. The supervising study surgeon will be present for key portions of the procedure. Residents or fellows may participate in procedures as is standard.

3. Patients will undergo standardized preoperative and postoperative education.
4. Patients will undergo standard postoperative care specific to the procedure performed, including enteral tube feeding while in the hospital until adequate nutrition by mouth is tolerated.

### **Standardization of Postoperative Care**

Standard protocols will apply while patients are admitted to the hospital. Once discharged from the hospital, patients will be evaluated at a routine postoperative appointment. Attending providers will be blinded as much as possible to the discharge tube feeding regimen.

## **H. MEASUREMENT**

The assessment instruments that will be used for specific aim 1:

1. EORTC QLQ-C30, Quality of life in cancer patients

The complications assessment instruments that will be used for specific aim 2:

1. HUM00012731 data collected around the time of operation and post-operative visit.
2. Long-term data from HUM00012731

Patients will also be invited to enroll in the “Patient outcomes following esophagectomy for benign and malignant disease” HUM00012731, a study in which the PI ([name]) is also a co-investigator. To minimize patient burden, the baseline preoperative assessment and the evaluation for quality of life will be performed according to the protocol outlined in HUM00012731. Demographics and history forms HUM00012731 will only be administered once preoperatively. This data will then be shared to support the study aims of this protocol to minimize patient inconvenience. In the event, that a patient does not wish to be co-enrolled in HUM00012731, the attached forms (EORTC QLQ-C30 and Demographics and history forms HUM00012731) will be administered by the Thoracic Surgery Clinical Coordinator, who will be trained and added to the HUM000XXXXX study protocol, at the scheduled time points outlined in Section N.

### **H.1 Primary Outcome Measures:**

#### **a. Specific Aim 1**

Quality of life data will be assessed pre-operatively and at the post-operative visit.

#### **b. Specific Aim 2**

Occurrence and severity of complications will be recorded by HUM00012731. Patients will be assessed at discharge and return visits. Adverse events following surgery (e.g, pneumonia, DVT, PE, anastomotic leak, atrial fibrillation, delirium, etc.) will be identified prospectively by the study team

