### **D. OUTCOME MEASURES**

The primary outcome measure for specific aim 1 will be the quality of life and patient satisfaction as measured by post-operative survey instruments.

Secondary Outcomes for specific aim 1:

- Complications following surgery (jejunal tube)
- Length of stay
- Costs

The primary outcome for specific aim 2 will be the occurrence of post-operative complications such as: atrial fibrillation, delirium, anastomotic leak, pneumonia within the 30-day post-operative time frame.

Secondary Outcomes for specific aim 2:

- Readmission rates and costs of care.

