## **H.2 Secondary Outcome Measures**

### **a. Specific Aims 1&2**

**1. Jejunostomy tube-specific** complications will also be identified prospectively. J-tube specific complications include infection, bowel obstruction that may require surgical repair, discomfort, diarrhea and dumping syndrome.

**2. Other outcome measures** (length of stay, readmission, etc.)

**3. Costs** will be determined retrospectively by reviewing the administrative billing data.

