## **I. DATA COLLECTION**

All data collection following surgery will be performed by research staff other than the study surgeon. This will reduce bias by maintaining masking in data collection of outcome measures. All research staff will be trained and certified to perform data collection procedures. Allowable windows for timed evaluations are specified in Section N and include a one-week window on each side of the postoperative visit planned at 2-3 weeks. The assessments at 1-month, 3-months, and 6-months will take place by mail and will not require a visit to the clinical site.

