**J. STATISTICAL AND DATA MANAGEMENT CONSIDERATIONS**

**For the specific aims:**

Specific Aim 1: Quality of Life measurements will be compared at 6 months, using descriptive statistics.

Specific Aim 2: Calories will be compared between groups.

**For the secondary aims:** Height and weight will be compared between groups at 30 days and 6 months.

**Sample size justification:** This was measured with the possible recruitment pool and differences between groups.

**Interim analysis:** At 50% recruitment or three years.

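### Death after randomization is not defined as an outcome and no rule covers it, so the complication, readmission and 6-month quality-of-life comparisons can favour the arm that loses more patients

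*Combined protocol and SAP*

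**What the plan says.** For Aim 2, Section D takes as primary outcome "the occurrence of post-operative complications such as: atrial fibrillation, delirium, anastomotic leak, pneumonia within the 30-day post-operative time frame". Section H.1b adds: "Occurrence and severity of complications will be recorded by HUM00012731", with assessment at discharge and return visits, and "Adverse events following surgery (e.g, pneumonia, DVT, PE, anastomotic leak, atrial fibrillation, delirium, etc.) will be identified prospectively by the study team". Both lists are open-ended and neither names death. H.2 lists other outcomes as "length of stay, readmission, etc" and says that costs "will be determined retrospectively by reviewing the administrative billing data".

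For Aim 1, Section J states: "Quality of Life measurements will be compared at 6 months, using descriptive statistics". Table 1 (Section N) also schedules the quality-of-life form at 2 weeks, 1 month and 3 months, but J names only 6 months. On the later contacts, Section I says: "The assessments at 1-month, 3-months, and 6-months will take place by mail". H.3 allows telephone or mail.

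Three other provisions bear on the point:

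- Section F places randomization before discharge or at POD#8, in patients who are eating adequately, and keeps randomized patients in their assigned group for analysis.
- Section K replaces patients who drop out or are lost to follow-up until a minimum number of evaluable patients is reached for both aims.
- Section B describes the operation as high risk, in patients whose condition may already be impaired.

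**The concern.** With a high-risk operation and 6 months of follow-up, deaths after randomization are foreseeable. The plan should say what each comparison does with them, and it does not.

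The gap matters because the outcomes do not treat death neutrally. Death before a readmission prevents the readmission. Death before 6 months removes the quality-of-life score. Death without another recorded complication may not register as an event at all. If the arms differ in deaths or non-response, an arm can look better because its sickest patients are no longer measured.

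**Working it through.** **Is there a figure to reproduce?** No. The sample size is a placeholder, and the documents give no alpha, power, effect size, SD, event rate or death rate. The text can be checked directly. The numbers below show direction only, and every rate in them is an assumption.

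**Step 1: where death could appear.** The aims (A), outcomes (D), complication list (H.1b), secondary outcomes (H.2), analysis statements (J) and Table 1 (N) name neither death, mortality nor vital status.

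**Step 2: would the schedule detect it?** The Adverse Events row of Table 1 starts at the 2-week clinic visit, so a patient who dies after discharge and before then has no return visit. Later contacts are remote. Without a vital-status item, an unreturned form from a patient who has died looks like non-response. Co-enrolment in HUM00012731 is optional. For patients who decline it, Section H names only the QLQ-C30 and the demographics and history forms.

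**Step 3: what the text allows for a death after randomization.**

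| Comparison | What can happen |
|---|---|
| 30-day complications (D, H.1b) | Recorded as an event under the open list, recorded as no event, or replaced under K |
| Readmission (D, H.2) | Not possible if death comes first; no rule |
| Costs (H.2) | Accrual stops at death, but a death during a readmission may be costly; no rule |
| 6-month quality of life (J) | No value; no rule |

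If replacement takes the patient out of the evaluable set, K conflicts with analysis by original group in F.

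**Step 4: complications.** Let p be the risk of a listed event and u the risk of death without one. Assume p = 28% in arm A and 30% in arm B, with u = 3% or 5% in A and 1% in B.

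- Deaths counted as no event: 28 − 30 = −2 points.
- Deaths counted as events: (28 + 3) − (30 + 1) = 0, or (28 + 5) − (30 + 1) = +2 points.
- Deaths replaced by patients like those who remain, p/(1 − u): 28/0.97 − 30/0.99 = 28.87 − 30.30 = −1.4 points, or 28/0.95 − 30/0.99 = 29.47 − 30.30 = −0.8 points.

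On these inputs the handling of death decides the direction. If u is 1% in both arms, the difference is −2 points whether or not death counts.

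**Step 5: readmission.** Assume 100 patients per arm and 20 readmitted or dead in each. If 4 of the 20 in one arm die before any readmission and none do in the other, readmission alone reads (20 − 4)/100 = 16% v 20%, while readmission-or-death is 20% v 20%. The arms do differ here, in deaths as well as in readmissions. Readmission alone shows only the half that favours the arm with the deaths.

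**Step 6: 6-month quality of life.** Let d be the share dead by 6 months, z_d the normal quantile of d, and rho the correlation between the risk of death and the score that would have been seen. The survivor mean exceeds the all-patient mean by rho × φ(z_d)/(1 − d) SD. At rho = 1:

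- d = 2%: 0.0484/0.98 = 0.049
- d = 5%: 0.1031/0.95 = 0.109
- d = 15%: 0.2332/0.85 = 0.274

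For rho from 0 to 1, the arm with more deaths therefore gains 0 to 0.06 SD at 5% v 2%, and 0 to 0.17 SD at 15% v 5%. The gain is zero if deaths are equal by arm or unrelated to quality of life.

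In points, and counting non-response with death: if 10% v 5% are lost and would have scored 30 points lower, the shift is 30 × 0.10 − 30 × 0.05 = 1.5 points.

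**The case against.** A reader might infer that the plan scores a patient who dies as complication-free, never readmitted and low-cost. The documents do not support that.

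- The lists in D, H.1b and H.2 are open, severity is recorded, and Table 1 has adverse-event contacts at 2 weeks and at 1, 3 and 6 months. A death could be captured through these.
- The forms of HUM00012731 are not in the documents, and it may already hold vital status.
- Under Section K a death might be replaced rather than counted as event-free.
- Absence of readmission, and low cost, follow only for a death before any readmission.

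More can be said on that side. Section J specifies calories as the Aim 2 analysis and gives none for complications, readmission or costs, so there the gap is in the outcome definitions rather than in a stated test. Patients who die before randomization enter neither arm, and those randomized are eating adequately, which may keep later deaths few. H.3 allows telephone contact, so non-response need not depend on returning a form. A repeated-measures model would not by itself settle quality of life, because it implicitly assigns scores after death.

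All of this stands, and it limits the point to undefined handling. It does not remove the point. An open list that may or may not include death leaves a primary outcome to be settled case by case, in a trial where treatment cannot be masked. The replacement rule adds a second way for deaths to leave the comparison.

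**Conclusion.** The concern holds in this form: death after randomization is neither an outcome nor covered by any rule, and the readings open to the analyst lead to different results. If deaths or non-response differ by arm, and for quality of life are also related to it, the comparisons can favour the arm with more losses. The direction for costs is not fixed.

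The size cannot be known from the documents. On the assumed rates above, the quality-of-life shift is at most 0.17 SD, and the complication difference moves by 2 to 4 points between not counting and counting deaths. With equal losses there is no such shift. This is a gap that should be closed before analysis; it does not show that the trial's result would be wrong.

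**What to change.** 1. In D and H.1b, count all-cause death after randomization as an event in the 30-day Aim 2 outcome. Report readmission-or-death alongside its separate components.
2. In Table 1, add vital status at each contact, taking it from HUM00012731 where that study already holds it. Report deaths by arm at 30 days and 6 months.
3. In K, state that patients who die or are lost after randomization are not replaced in the analysis and stay in their original group, consistent with F.
4. In J, use all scheduled post-operative QLQ-C30 scores (2 weeks, 1, 3 and 6 months) in a repeated-measures model, to handle missing forms among patients who are alive. Tabulate deaths by arm beside it, and add an analysis that ranks death as the worst outcome, since the model alone does not deal with death.

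The cost is a few sentences, one Table 1 row and slightly more analysis work on scores already scheduled. The one drawback is that a composite including death can hide opposing effects, so its components must be shown.

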## **H.2 Secondary Outcome Measures**

### **a. Specific Aims 1&2**

**1. Jejunostomy tube-specific** complications will also be identified prospectively. J-tube specific complications include infection, bowel obstruction that may require surgical repair, discomfort, diarrhea and dumping syndrome.

**2. Other outcome measures** (length of stay, readmission, etc.)

**3. Costs** will be determined retrospectively by reviewing the administrative billing data.

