**Protocol 01**

**06/16/2014**

## A. STUDY AIMS

Specific Aim 1: To determine if routine dietary supplementation with enteral tube feeding affects recovery and quality of life after esophagectomy. Medicare rules only pay for enteral supplements (tube feeding) if the patient needs alternative feeding for greater than 3 months. Many insurers have adopted these rules, without evidence in post-operative patients.

- We hypothesize that routine post-operative supplementation will enhance patients recovery and quality of life, by increasing the time of adequate nutrition.

Specific Aim 2: To determine the occurrence of common complications and readmissions post-operatively between patients who are routinely discharged with tube feeding and those that are not. If patients are not discharged with tube feeds, they must obtain all of their nutrition by mouth, which may be difficult in the early post-operative period.

- We hypothesize that routine use of tube feeding may reduce the occurrence of complications.

The secondary aims of this randomized clinical trial are:

- To compare costs of care between groups.
- To assess how length of stay (LOS) and readmission rates are affected by routine use of tube feeding, as well as costs of care.
- Rates of occurrence of tube feeding or jejunal tube-specific complications

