## B. BACKGROUND AND SIGNIFICANCE

Nutritional support is taking on an increasing focus in peri-operative surgical care. It is particularly important in esophageal resection, which is a high-risk operation in a patient population whose pre-operative condition may be reduced due to pre-operative chemo- and radio-therapy, as well as dysphagia from the cancer. Post-operatively, patients are routinely cleared to take nutrition by mouth once an esophagram is done post-operative day 7 and shows no abnormality.

Tube feeding should be at goal by day 7, but is discontinued once patients are discharged, as long as they are able to eat, i.e., do not have evidence of anastomotic leak or other serious complications. The amount patients are able to eat is frequently variable, and is not well recorded prior to or after discharge. There may be a dip in calories consumed, which if severe, will lead to readmission for

hydration, failure to thrive, or possibly the development of a post-operative complication.

Currently all patients are discharged with the jejunal feeding tube placed at the operation, just in case they are unable to eat post-operatively due to an unforeseen complication. Since many insurers and Medicare require patients to pay for tube feeding needed for less than three months (~\$800/month and up, plus the services of a home health nurse), we do not routinely require patients use the feeding tube once discharged.

For esophagectomy specifically, and upper gastro-intestinal surgery in general, there is very limited literature looking at this question. Small randomized studies have not shown a benefit to routine tube feeding, although the numbers were very small, ranging from 12 to 70 in each group. Furthermore, the duration of tube feeding averaged 14 days, and even in the groups being fed enterally, were not meeting caloric needs in the period studied.

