### **C. STUDY SCHEMA**

Patients will be evaluated for surgery by the study surgeons. Patients scheduled to undergo an elective esophagectomy and who meet inclusion criteria (See Section E.1) will be approached for enrollment. Written informed consent will be obtained from all enrolled patients (see Appendix B). Pre-operative Quality of Life Survey will be obtained using the EORTC QLQ-C30 (see attached). Patients will then be randomly assigned to either routine post-operative tube feeding for 1 month, or usual practice, tube feeding to continue in the hospital until the patient is taking adequate nutrition by mouth at POD#8, or upon discharge. Since this study cannot be blinded, patients that cannot take nutrition by mouth at POD#8, or are tube feeding dependent on discharge will not be included in analysis.

Figure 1. Illustrates the study design

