## **F. RANDOMIZATION AND MASKING**

Randomization envelopes will be created at the start of the study. Each envelope will be opened prior to discharge or at POD#8 if patients are able to take adequate nutrition by mouth, to determine if post-operative tube feeding will be continued or not.

By consenting to the study, patients agree to continue tube feeding for at least 50% of caloric needs for 1 month post-operatively. Cross-over after randomization will be permitted for patient condition, although once randomized, patients will be analyzed by the original group.

- A copy of the signed research consent form must be included in the patient's hospital chart.

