#### **O. RESEARCH COSTS**

Costs incurred by the study will be borne by unrestricted Section of Thoracic Surgery research funds. Only those patients with insurance that does not cover the post-operative tube feeding will be paid for by the Section of Thoracic Surgery. There are no costs for data collection that will be charged to the patient.

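### The cost comparison names only billing data as its source and does not say whether home tube feeding is counted; anything missed would favour the feeding arm

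*Combined protocol and SAP*

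**What the plan says.** Section A lists among the secondary aims "To compare costs of care between groups", and section D lists costs among the secondary outcomes of both specific aims. The only statement on measurement is in section H.2, item 3: costs "will be determined retrospectively by reviewing the administrative billing data". It does not say whose billing data are meant, which components count, or from whose perspective. Section J does not fill the gap, since its line on the secondary aims covers only height and weight. Table 1 in section N has a single costs entry, at 6 months, and no row for days of home feeding or nursing visits.

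On what differs between the arms, section C has patients "randomly assigned to either routine post-operative tube feeding for 1 month, or usual practice".

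On who pays:
- Section A: "Medicare rules only pay for enteral supplements (tube feeding) if the patient needs alternative feeding for greater than 3 months".
- Section B: "many insurers and Medicare require patients to pay for tube feeding needed for less than three months". It gives a price of about $800 a month and up, "plus the services of a home health nurse". The nursing is not priced.
- Section O: "Only those patients with insurance that does not cover the post-operative tube feeding will be paid for by the Section of Thoracic Surgery".

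**The concern.** A month of tube feeding, most or all of it at home, is the intervention. Its cost therefore belongs in any comparison meant to show what routine feeding costs or saves. The protocol itself gives reason to doubt that a billing extract would hold all of it: feeding for under three months is often not covered, and in the trial the uncovered part is met from research funds. Section O settles who pays, not whether the payment is counted.

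If home feeding is missing from the extract, the comparison would credit the feeding arm with any billed savings from fewer readmissions or complications and leave out part of the cost of achieving them. Payer coverage of short-term feeding is part of the trial's stated motivation, so readers are likely to use the cost result for that question. Days fed are also hard to reconstruct at 6 months if nobody recorded them along the way.

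**Working it through.** The documents give no cost total, standard deviation, expected saving or sample size, so there is no figure to reproduce. The arithmetic below shows scale only.

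**Inputs from the documents**
- Base price P = $800 a month (section B, where it is a lower figure and excludes nursing).
- Duration d. Section C's wording suggests a full month after assignment, taken as 30 days. Section F counts the month from the operation. It also says "Each envelope will be opened prior to discharge or at POD#8", which leaves 30 − 8 = 22 days if home feeding starts at day 8.

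**Assumptions, not in the documents**
- A 30-day month.
- u, the share of home-feeding cost that the billing data miss: 0 to 1, the same in both arms.
- c, the share of usual-care patients who resume feeding for the same duration: 0 to 0.3. Sections F and L permit cross-over and analyse patients by original group, but give no rate.
- All feeding-arm patients complete the month.

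**Step 1. Understatement of the feeding arm, per patient** = P × u × d/30

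| u | d = 30 | d = 22 |
|---|---|---|
| 0 | $0 | $0 |
| 0.25 | $200 | $147 |
| 0.50 | $400 | $293 |
| 0.75 | $600 | $440 |
| 1 | $800 | $587 |

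For example, 800 × 1 × 22/30 = $586.67.

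**Step 2. Bias in the between-arm difference.** Usual-care patients who resume feeding are undercounted too, by P × u × c × d/30 on average. The difference (feeding minus usual care) is therefore understated by P × u × (1 − c) × d/30. For d = 30:

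| u | c = 0 | c = 0.1 | c = 0.2 | c = 0.3 |
|---|---|---|---|---|
| 0 | $0 | $0 | $0 | $0 |
| 0.5 | $400 | $360 | $320 | $280 |
| 1 | $800 | $720 | $640 | $560 |

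**Step 3. Direction and what is left out.** With the same u in both arms, the bias favours tube feeding as long as fewer usual-care than feeding-arm patients use home feeding. It is smaller if feeding-arm patients stop early or spend days after day 8 in hospital. It is also smaller if the $800 price reflects fuller feeding than the trial delivers, since section F requires only at least half of caloric needs. It is larger at higher prices and once nursing is added.

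**The case against.** The strongest reply is that no harm has been shown. Section H.2 does not limit billing data to hospital bills. Payer or home-care claims could qualify, and with full capture the bias is $0. The plan does not expressly rule out another source, and Section payment records could later supply the research-paid part. A billed-care perspective that leaves home feeding out can also be legitimate. On this view the plan has an undefined cost outcome, not a biased one, and one sentence on perspective would be enough.

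Most of this stands. A reader might infer that home feeding is absent from the billing data, or that the cost result will be wrong. The documents support neither, because they do not say what the data contain. A reader might also take section O to mean that research payments are kept out of the cost outcome, but it speaks only of funding.

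Two things remain. First, a billed-care perspective has to be declared, and none is. Second, declaring it would not let anyone find out what the omission is worth. Section records would cover only feeding that insurance does not pay for, the plan does not say they will be used, and no source is named for the rest. That justifies recording days fed prospectively as well as adding a sentence.

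A further fair point is masking. Section I wants masking kept in outcome data collection, and asking about home feeding can reveal the arm. The fix has to allow for this.

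**Conclusion.** The concern holds in conditional form. The plan compares costs between arms, names one source, and does not say whether the resource that defines the intervention is in it. To the extent it is not, the cost comparison is biased toward tube feeding.

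At $800 for a full month without nursing, the feeding arm is understated by between $0 and $800 per patient ($0 to $587 for 22 days). If nothing is captured, the between-arm bias for a full month runs from $800 with no resumed feeding in usual care to $560 with 30%. These figures rest on assumed values of u and c and on the protocol's base price.

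Whether the bias would change the cost conclusion cannot be judged, because the documents give no total cost, variability or expected saving. A reader might extend the doubt to quality of life or complications; nothing here supports that, since neither is measured from billing data. This is a cheap improvement of low severity.

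**What to change.** In section H.2, item 3, specify two between-group comparisons and state the perspective of each:

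- **(a)** Billed costs through 6 months.
- **(b)** Billed costs through 6 months with any home-feeding items removed, plus home formula, supplies and nursing. Value these as days fed and nursing visits times one common stated unit price for each. Apply this to every patient in both arms, including cross-overs and whoever paid.

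Removing the billed home-feeding items before adding the valued ones prevents double counting. Section payment records should serve only to set or check the unit price, so that valuation does not vary with the payer.

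Add one row to Table 1 for home tube-feeding days and nursing visits at the contacts already planned (2 weeks and 1, 3 and 6 months). Collect it after the quality-of-life and adverse-event items at each contact.

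The cost is a little data work, including identifying home-feeding items in the billing extract. A nursing price must be sourced, since the documents give none. Days fed do not measure the amount fed. Some risk of unmasking remains, because a collector who learns the arm at one contact may carry it to the next. The cost figure for the feeding arm may also look less favourable.
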